### 2.3.1 Risk Assessment

Potential Risk of Clinical Significance	Summary of Data/Rationale for Risk	Mitigation Strategy
Study Intervention (s): BD Spinal NRFit™ Needles and BD Spinal NRFit™ Sets		
Complications vary based upon anatomic site and clinician experience and may include: 

•localized/systemic infection,

•exposure to bodily fluids and/or bloodborne pathogens,

•subarachnoid/subdural/epidural (spinal) hematoma,

•herniation,

•low back pain,

•paresthesia,

•accidental puncture of the dura,

•post dural puncture headache,

•total subarachnoid block,

•seizures,

•pneumocephalus,

•nerve injury,

•cerebral ischemia or hemorrhage,

•bladder dysfunction from prolonged blockade,

•cauda equine syndrome,

•transient neurologic symptoms,

•adhesive arachnoiditis,

	A benefit-risk assessment for the overall medical device is documented in the Risk Management Report. All risks and combinations of risks were reviewed, and it has been determined that all are within acceptable limits. The benefits of the device outweigh each risk individually as well as any combination of risk and are consistent with the use of the devices. Therefore, the devices are considered safe for their intended use. These risks are identified as residual risks and are disclosed to the end user.	Only participants requiring a Spinal needle device as part of their standard medical care will receive a device. The treating physician will select the most appropriate device for the participants based on their specific needs. The general guidelines “aseptic technique and proper preparation are essential” and “observe universal precautions with all patients” are included in the BD Spinal NRFit™ needles and in the BD Spinal NRFit™ Sets IFUs.  Only physicians experienced in performing procedures using Spinal Needles and Spinal Needle Sets should perform neuraxial anesthesia procedures. A caution statement, “To be used by properly qualified and trained healthcare professionals”, is included in the BD Spinal

Potential Risk of Clinical Significance	Summary of Data/Rationale for Risk	Mitigation Strategy

 
•anterior spinal artery syndrome,
 
•acute neuropathic pain,
 
•damage to CNS blood vessels,
 
•AV fistula formation,
 
•spinal cord ischemia,
 
•permanent neurological injury,
 
•paraplegia,
 
•hypotension,
 
•cardiovascular collapse,
 
•death.
 
		NRFit™ needles and in the BD Spinal NRFit™ Sets IFUs. See device specific IFU for additional information.
Study Intervention (s): BD Spinal Introducer NRFit™ Needle		

Complications vary based upon anatomic site and clinician experience and may include:
 
 
•localized/systemic infection,
 
•exposure to bodily fluids and/or bloodborne pathogens,
 
•low back pain,
 
•accidental puncture of the dura,
 
•post dural puncture headache.
 
	
A benefit-risk assessment for the overall medical device is documented in the Risk Management Report. All risks and combinations of risks were reviewed, and it has been determined that all are within acceptable limits. The benefits of the device outweigh each risk individually as well as any combination of risk and are consistent with the use of the devices. Therefore, the devices are considered safe for their intended use. These risks are identified as residual risks and are disclosed to the end user.
	
Only physicians experienced in performing procedures using Spinal Introducer Needles should perform neuraxial anesthesia procedures. A caution statement, “To be used by properly qualified and trained healthcare professionals”, is included in the BD Spinal Introducer NRFit™ needle IFU. See device specific IFU for additional information.

Study Intervention (s): BD Syringes NRFit™		

Potential Procedure Related Complications:
 
 
•Pain,
 
•exposure to bloodborne pathogens,
 
•potential for infiltration/extravasation, particulate embolism,
 
•air embolism,
 
•localized/systemic infection,
 
•death.
 
	
A benefit-risk assessment for the overall medical device is documented in the Risk Management Report. All risks and combinations of risks were reviewed, and it has been determined that all are within acceptable limits. The benefits of the device outweigh each risk individually as well as any combination of risk and are consistent with the use of the devices. Therefore, the devices considered safe for their intended use. These risks are identified as residual risks and are disclosed to the end user.
	
The IFUs report that Syringes are intended for neuraxial use by healthcare professional. The caution statements, “Observe syringe carefully during procedures” and “Always inspect the package before opening” are included in the BD Syringes NRFit™ IFUs. The general guidelines “aseptic technique and proper preparation are essential” and “observe universal precautions with all patients” are included in the BD Syringes NRFit™ IFUs.

Potential Risk of Clinical Significance	Summary of Data/Rationale for Risk	Mitigation Strategy
Leakage resulting in an inaccurate dose or exposure to medicine and bodily fluids.		A general guideline “An ISO 80369-6 compliant syringe tip cap can be used to prevent leakage of fluids or medications from the syringe” is included in the BD Syringes NRFit™ IFUs. See device specific IFU for additional information.
Study Procedures		

No study-specific risks identified, compared to any neuraxial procedure as part of standard medical care. Neuraxial procedures maybe associated with the following risks:
 
 
•Inadequate or failed anesthesia
 
•Hemodynamic changes, most commonly hypotension
 
•Post-dural puncture headache
 
•Localized pain
 
•Localized skin irritation
 
•Urinary retention (temporary)
 
•Nerve injury (rare)
 
•Spinal-epidural hematoma (rare)
 
•Infection
 
 
Potential procedure complications with the ancillary devices:
 
 
•Redness
 
•Irritation
 
•Pain
 
•Bleeding
 
•Anxiety
 
•Syncopal episode
 
•Granuloma
 
•Hematoma
 
•Paresthesia
 
•Exposure to bloodborne pathogens
 
•Potential for infiltration/extravasation
 
•Particulate embolism
 
•Localized/systemic infection
 
•Floater
 
	
See Clinical literature [10]; [11]; [12]; [13]; [14] for additional information.
	
 
•Physicians should select the smallest diameter needle sufficient to support the specific procedure
 
•Patient blood pressure and heart rate should be closely monitored throughout the procedure and after medication administration
 
•Only physicians with sufficient training and experience should perform neuraxial anesthesia procedures
 
 
The warning statements, “Aseptic technique and proper preparation are essential” and “Percutaneous puncture with a contaminated needle may lead to serious illness, or other infectious diseases” are included in the Blunt Fill NRFit™ Needles and Blunt Filter NRFit™ Needles IFUs. See device specific IFU for additional information.

### 2.3.2 Benefit Assessment

There is no direct benefit for study participation for an individual patient other than the placement of one of the study devices.

### 2.3.3 Overall Benefit: Risk Conclusion

There is no anticipated additional risk associated with the device use or any study procedure due to participation in this study compared to any BD Spinal NRFit™ Needles, the BD Spinal Introducer NRFit™ Needles, BD Spinal NRFit™ Needle Sets, and the BD Syringes NRFit™ use as part of standard medical care.

## 3 OBJECTIVES AND ENDPOINTS

Objectives	Endpoints
Primary Performance	

 
• To assess the performance of the BD Spinal NRFit™ needles and BD NRFit™ introducers used in spinal anesthesia procedures.
 
• To assess the performance of BD NRFit™ Syringes when used in spinal anesthesia procedures.
 
	
 
• Percentage of participants with successful placement of the BD Spinal NRFit™ needle in the subarachnoid location defined as the spontaneous appearance of cerebrospinal fluid (CSF) emerging from the spinal needle hub.
 
• Percentage of participants with successful placement of the BD Spinal NRFit™ needle in the subarachnoid location defined as the spontaneous appearance of cerebrospinal fluid (CSF) emerging from the spinal needle hub when an BD NRFit™ introducer is used.
 
• Percentage of participants with successful aspiration and injection of anesthetic through a BD NRFit™ Syringe.
 
• Percentage of participants with BD NRFit™ Syringes that do not leak at the connection point during medication administration.
 

Objectives	Endpoints

Primary Safety
 
 
• To assess the incidence of post dural puncture headache (PDPH).
 
• To assess the incidence of any BD NRFit™ spinal needle and BD NRFit™ introducer and BD NRFit™ syringe and procedure-related adverse events (other than PDPH).
 
	
 
• Percentage of participants with a diagnosis of PDPH (defined as headache that worsens when standing/upright position and relieves when laying supine) for a period of up to 10 (<math>\pm 3</math> days)* days following the procedure.
 
• Incidence of device/procedure-related adverse events.
 
 
*The time window of <math>\pm 3</math> days must be used when the 10-day post-procedure occurs during the weekends or holidays.

### 3.1 Acceptance Criteria

Acceptance criteria are anticipated for the following objectives:

- Relevant literature for the state-of-the-art generic device group- spinal needle and spinal introducer needle supports the predefined clinical performance objectives, success rate in placing the needle in the subarachnoid space and obtaining CSF. Confirmation of the spontaneous appearance of cerebrospinal fluid (CSF) emerging from the spinal needle hub. The Primary efficacy endpoint is the spontaneous appearance of CSF with the expected rate ranging  $\geq 90\%$  [15], [16], [17], [18], [19] and [20].
- Relevant literature for the state-of-the-art generic device group- spinal needle and spinal introducer needle supports the predefined clinical safety objectives, incidence of Post Dural Puncture Headache (PDPH)  $\leq 3\%$  within 7 days following spinal procedure. In the state-of-the-art literature several studies investigated incidence of PDPH, it ranges from 0% to 28.12%. All cases occurred within 7 days following the procedure [15], [16], [17], [18], [21], [22], [23], [24], [25], [26], [27], [28], [29], [30], [31], [32], [33], [34], [35], [36], [37], [38], [39], [40], [41], [42], [43], [44].
- Relevant literature for the state-of-the-art generic device group- spinal needle and spinal introducer needle supports the predefined clinical safety objectives, preventing misconnection and wrong route medication delivery misconnections or wrong route administration of medication has prompted the introduction of ISO 80369, NRFit needles [45], [46], [47], [48], [49], [50], [51], [52], [53].

Other acceptance criteria are:

- Incidence of misconnection 0%
- Incidence of medication leak at BD NRFit™ syringe connection point  $< 2\%$
- Incidence of aspiration/injection through a BD NRFit™ syringe  $> 80\%$

## 4 STUDY DESIGN

### 4.1 Overall Design

This is a multi-center, prospective, open label, single arm post-market study that will enroll approximately 180 participants in order to have a minimum of 150 treated participants who will receive a spinal anesthesia procedure as part of their routine medical care. A minimum of 50 participants for each of the two needle tip types (Quincke and Whitacre tip) will be enrolled in the study. Data related to the safety and performance of the BD Spinal NRFit™ Needles, the BD Spinal Introducer NRFit™ Needles, the BD Spinal NRFit™ Needle Sets, the BD Syringes NRFit™ and ancillary devices will be captured when used as intended.

Participants will be screened against eligibility criteria and will be considered enrolled once the informed consent document is signed. The procedure(s) performed, and device(s) used, will be left to the discretion of the participant's physician investigator.

Participants will be followed from the time of spinal procedure for up to 10 days ( $\pm$  3 days) post spinal procedure to assess for any adverse events/complications. If the participant has been discharged from the hospital prior to day-10 ( $\pm$  3 days) post procedure, follow-up may be performed in a variety of ways including by telephone. The site staff must take advantage of the time window of  $\pm$  3 days only when the 10-day post-procedure occurs during the weekends or holidays. However, any adverse event or complication must be diagnosed and confirmed by a study physician.

Additionally, to assess overall ease of spinal procedure, the clinician performing the procedure will complete a brief survey describing their experience with the procedure.

The total duration of the study is expected to be approximately 49-51 weeks from first participant enrolled up to last participant having last visit.

### 4.2 Scientific Rationale for Study Design

This study is designed to collect clinical data on the safety and performance of the BD Spinal NRFit™ Needles, the BD Spinal Introducer NRFit™ Needles, the BD Spinal NRFit™ Needle Sets, and the BD Syringes NRFit™ devices. The usage of the study and ancillary devices, according to its intended use will ensure that study activities have no direct impact on the endpoints being assessed and that they represent outcomes typically associated with the intended medical use of the study devices in clinical practice.

#### 4.2.1 Participant Input into Design

Not applicable. Participant input was not sought while designing the study.

### 4.3 End of Study Definition

A participant is considered to have completed the study if he/she has completed all phases of the study including the day-10 ( $\pm$  3 days) post procedure follow-up assessment.

The end of the study is defined as the date of the last study assessment of the last participant in the study.

## 5 STUDY POPULATION

Participants will be recruited from the patient population treated at the investigational sites.

Sites may choose to limit recruitment to specific areas of the hospital and/or to patients treated by specific healthcare providers.

### 5.1 Inclusion Criteria

In order to be eligible to participate in this study, an individual must meet all of the following criteria:

1. Any patient, regardless of age or gender, for which the investigator has decided that a neuraxial procedure must be performed utilizing BD NRFit™ Spinal Needles, NRFit™ Spinal Introducer Needles, and NRFit™ Syringes as part of their routine medical care.
2. Expected to be available for observation through the study period (10 days,  $\pm$  3 days, post procedure\*).
3. Able and willing to provide signed and dated informed consent or legal authorized representative (LAR) authorized to give consent on behalf of the participant (Note: Consent of guardian or parent may be required for participants under the age of 18 years; participant assent may be required as well).

\*The time window of  $\pm$  3 days must be used when the 10-day post-procedure occurs during the weekends or holidays.

### 5.2 Exclusion Criteria

Participants are excluded from the study if any of the following criteria apply:

1. Coagulopathy or bleeding disorder, where it is in the opinion of the investigator makes regional anesthetic of increased risk.
2. Subjects with a history of neurological impairment of the trunk or lower extremities.
3. Infection at the site of needle insertion.
4. Previous spine surgery at the level involved in the study procedure.

### 5.3 Lifestyle Considerations

Not applicable. There are no study-specific restrictions other than those typically associated with use of a study devices (e.g., keeping the insertion area clean and dry).

### 5.4 Screen Failures

Screen failures are defined as participants who consent to participate in the clinical study but have not subsequently met the eligibility criteria. Data on informed consent, age, sex assigned at birth, and reason of screening failure will be collected. Additional information may also be collected if appropriate.

Individuals who do not meet the criteria for participation in this study (screen failure) may not be rescreened.

## 5.5 Vulnerable Population

As the instruction for use of the BD NRFit™ Spinal Needles, BD Spinal NRFit™ Needle Sets, BD NRFit™ Spinal Introducer Needles, and BD NRFit™ Syringes does not foresee any limitations in terms of subject age or status and the study aims to collect data on clinical use, the study will also consider participants under 18 years of age, or participants requiring a legal authorized representative. In addition, pregnant and breastfeeding subjects are not excluded from study participation. As the study devices will be used as intended, this population is considered to be not exposed to any additional risk due to study participation.

Some participating clinical sites may decide to not include vulnerable subjects as per their hospital policy or may not include minors as the participating department treats only adults.

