## **7.4 Follow-Up**

Participants will be followed through 10-days ( $\pm$  3 days) post procedure to assess for adverse events/complications. Assessments may be performed in a variety of ways, including by telephone, if the participant has been discharged from the hospital prior to day-10 post procedure. The site staff must take advantage of the time window of  $\pm$  3 days only when the 10-day post-procedure occurs during the weekends or holidays. Any adverse event or complication must be diagnosed and confirmed by a study physician. Additional information may also be collected if appropriate.

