### **7.4.1 Follow-Up data**

During the required follow-up period the following data will be collected:

- Adverse events/complications

- Post-dural puncture headache (PDPH)

Since there are many causes of headache, it is important that the physicians make the diagnosis of Post Dural-Puncture Headache after sufficient evaluation and being reasonably certain that is the cause of the headache. Post-dural puncture headache is defined as a headache which occurs in the upright/standing position and is relieved when the participant is lying down, provided no other cause of headache could be identified. PDPH is a headache occurring within 5 days of a lumbar puncture, caused by cerebrospinal fluid (CSF) leakage through the dural puncture. It is usually accompanied by neck stiffness and/or subjective hearing symptoms. It remits spontaneously within 2 weeks, or after sealing of the leak with autologous epidural lumbar patch [55]. Participants will be questioned for the presence, severity, onset, duration, and characteristics of headaches, and any other complications. The severity of the headache will be graded from none to mild, moderate, or severe as following [56]:

- None: No PDPH
- Mild: when PDPH caused no interference with daily activities and was treated with no medication or oral analgesics.
- Moderate: when PDPH caused a patient difficulty in performing daily activities and was treated with oral analgesics.
- Severe: a headache that resulted in the patients being unable to perform his or her daily activities or being confined to bed and requiring oral or IV analgesic and/or epidural blood patch for treatment.

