4.0 ANALYSIS POPULATION SET(S)

4.1 Populations Definitions

The following populations are defined in the table below:

Table 4. Population Definitions

Population	Description
Enrolled	All participants who sign the ICF
Treated	All participants in whom a spinal anesthesia procedure is attempted, regardless of success
Safety	All participants in whom a spinal anesthesia procedure is successful

Treated population will include the following participants on the Spinal Procedure CRF page:

- 'Was spinal procedure performed or attempted using BD NRFit devices?' Equals 'Yes'.

Safety population will include the following participants on the Spinal Procedure Details - BD NRFit Needle CRF page:

- 'Was there a spontaneous appearance of cerebrospinal fluid (CSF) emerging from the needle hub?' Equals 'Yes'.

The primary performance endpoints analysis will be performed on the treated population. The primary safety endpoint analysis for PDPH incidence will be performed on the safety population. The primary safety endpoint analysis for device/procedure-related adverse events (other than PDPH) will be performed on the treated population.

THIS SUBJECT MATTER IS RESTRICTED SOLELY FOR THE USE OF BECTON DICKINSON AND COMPANY AND ITS SUBSIDIARIES

 BD	Statistical Analysis Plan	Page No.
	Study ID: MDS-21NRFit001	7 of 13

GFM-10082C

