5.2.2 Primary Safety Endpoints

- Incidence of post dural puncture headache (PDPH)

The event of PDPH is defined as headache that worsens when standing/upright position and relieves when laying supine for a period of up to 10 (\pm 3 days) days following the procedure.

The incidence of PDPH will be based on response to the following question:

- "Post-dural Puncture Headache" CRF page: "Did the subject develop post-dural puncture headache (PDPH)?" Equals 'Yes'

Participants experiencing any severity (mild/moderate/severe) of PDPH will contribute to the incidence count in the numerator.

The incidence rate for the above primary safety endpoints will be calculated as the number of participants experiencing the event divided by the total number of safety participants defined in section 4.1; 95% confidence interval (exact method) will be calculated.

- Incidence of any BD NRFit™ spinal needle and BD NRFit™ introducer and BD NRFit™ syringe and procedure-related adverse events (other than PDPH)

Subject will be considered as having an event if the subject has the following responses for the questions on the AE CRF Page listed below:

THIS SUBJECT MATTER IS RESTRICTED SOLELY FOR THE USE OF BECTON DICKINSON AND COMPANY AND ITS SUBSIDIARIES

 BD	Statistical Analysis Plan	Page No.
	Study ID: MDS-21NRFit001	10 of 13

GFM-10082C

- Relationship to procedure: Equals 'Possible' or 'Probable' or 'Causal' OR
Relationship to spinal needle: Equals 'Possible' or 'Probable' or 'Causal'
OR Relationship to syringe: Equals 'Possible' or 'Probable' or 'Causal' OR
Relationship to introducer: Equals 'Possible' or 'Probable' or 'Causal'

The incidence rate for the above primary safety endpoints will be calculated as the number of participants experiencing the event divided by the total number of treated participants; 95% confidence interval (exact method) will be calculated.

THIS SUBJECT MATTER IS RESTRICTED SOLELY FOR THE USE OF BECTON DICKINSON AND COMPANY AND ITS SUBSIDIARIES

 BD	Statistical Analysis Plan	Page No.
	Study ID: MDS-21NRFit001	11 of 13

GFM-10082C

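### The PDPH rate is divided by all safety participants, including any who cannot report a posture-dependent headache, and neither document says how such participants are assessed or counted

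*Protocol*

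**What the plan says.** **Who is eligible.** Protocol 5.1 admits "Any patient, regardless of age or gender, for which the investigator has decided that a neuraxial procedure must be performed". Protocol 5.5 adds that "the study will also consider participants under 18 years of age, or participants requiring a legal authorized representative". It also leaves room to opt out: "Some participating clinical sites may decide to not include vulnerable subjects as per their hospital policy". No number or cap is set for these groups.

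**How PDPH is found.** Protocol 7.4.1 defines PDPH as a headache that appears upright and eases on lying down, with no other cause identified. It says that "Participants will be questioned for the presence, severity, onset, duration, and characteristics of headaches, and any other complications". After discharge this may be done by telephone. Protocol 7.4 also requires that "Any adverse event or complication must be diagnosed and confirmed by a study physician". Neither document describes a caregiver-reported, observational or age-adapted assessment.

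**How the rate is computed.** SAP 5.2.2 takes the numerator from a 'Yes' to the CRF question "Did the subject develop post-dural puncture headache (PDPH". The count is "divided by the total number of safety participants defined in section 4.1". SAP 4.1 defines that population as "All participants in whom a spinal anesthesia procedure is successful" and identifies it on the CRF by CSF appearance alone. SAP 5.1 lists no derived variables, so there is no assessable subset.

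**What the result is compared with.** SAP 1.3 asks for an observed PDPH incidence of at most 3%.

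**Missing data.** Protocol 10.4 says analyses use evaluable data. It does not say what evaluable means for PDPH, and the SAP neither repeats the rule nor fits it to its own denominator.

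**The concern.** The endpoint depends on a symptom that the participant has to describe, but membership of its denominator does not depend on being able to describe it. Under the SAP rule, anyone in the safety population who is not marked 'Yes' is in effect event-free. For a participant who cannot convey a headache or its relation to posture, a 'No' records absence of information rather than absence of PDPH.

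Such a participant can complete the day-10 contact and have a form filled in, so ordinary missing-data handling need not catch the problem. The effect is to lower a primary safety rate that is judged against an upper limit. Its size would depend on how many such participants each site enrols, which the plan leaves to the sites.

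**Working it through.** **Inputs**
- Planned size 150 treated, and 150 in the precision row at a 3% rate (Protocol 10.2, SAP 2.4).
- Criterion: observed PDPH at most 3% (SAP 1.3).
- 95% exact confidence interval (SAP 5.2.2).
- Share f of safety participants who cannot report a postural headache: **assumed**, because the documents give no figure. Values of 5%, 10% and 20% are shown; zero is possible.
- **Assumed**: the underlying PDPH rate is the same in those who cannot report, and none of them is recorded as 'Yes'.

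**Step 1: the plan's own figures.** The chance of at least one event at a 1% rate in 150 is 1 − 0.99^150 = 77.85%, against 77.9% stated. The exact half-width at 3% and n = 150 is 3.12%, against 3.1% stated. Both reproduce.

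**Step 2: dilution.** Observed rate = true rate × (1 − f).

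| f | True 3.0% reads as | True rate that reads as 3.0% |
|---|---|---|
| 5% | 3.0 × 0.95 = 2.85% | 3.0 / 0.95 = 3.16% |
| 10% | 3.0 × 0.90 = 2.70% | 3.0 / 0.90 = 3.33% |
| 20% | 3.0 × 0.80 = 2.40% | 3.0 / 0.80 = 3.75% |

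**Step 3: when the pass/fail result changes.** With 150 in the denominator the criterion allows at most 4 events, since 4/150 = 2.67% and 5/150 = 3.33%. Take the 4 events as fixed and remove m non-assessable participants:
- m = 15: 4/135 = 2.96%, still met
- m = 16: 4/134 = 2.99%, still met
- m = 17: 4/133 = 3.01%, not met

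So 17 of 150, about 11%, are needed. Four events is the most sensitive count. Five events fail on either denominator, and 3 events would need more than 50 removed (3/100 = 3.0%).

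**Step 4: against sampling error.** The exact 95% interval for 4/150 is 0.73% to 6.69%. For 4/135 it is 0.81% to 7.41%, and for 4/120 (3.33%) it is 0.92% to 8.31%.

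**Step 5: chance of meeting the criterion when the true rate is 5%.** With 30 of 150 non-assessable, events arise among the other 120. Dividing by 150 allows up to 4 events, with probability 27.8%. Dividing by 120 allows up to 3 (3% of 120 = 3.6), with probability 14.4%. With 15 non-assessable, both denominators allow up to 4 events and the probability is 19.0% either way.

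**The case against.** The strongest reply is that the documents do not fix what is recorded for a participant who cannot report. PDPH is a physician's diagnosis made after evaluation, follow-up may take several forms, and nothing bars a caregiver's account or direct observation. The CRF itself is not in the documents, and the evaluable-data rule in Protocol 10.4 could remove a blank answer. A reader might infer that every such participant is entered as 'No'. The documents do not support that; they support a tendency. What stands is that any such workaround is left to each site, that Protocol 7.4.1 wants the physician reasonably certain of the cause (which favours 'No' when the symptom cannot be described), and that the SAP denominator keeps the participant whatever was recorded.

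A reader might also equate being under 18, or needing a representative, with being unable to report. That does not follow. The protocol provides for assent by minors, and the literature cited for the PDPH criterion in Protocol 3.1 includes studies in children. Nor do the infant examples in the ASA table or the short needles in Appendix 16.1 show that infants will be enrolled: the first is a general classification, the second a list of available variants.

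A reader might multiply 150 by the 90% placement criterion and work with 135 safety participants, where removing two changes the result at 4 events (4/133). The plan does not state 135. The 90% is a minimum threshold, and the plan's own 3% row uses 150.

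Finally, the dilution formula needs equal underlying rates. If PDPH is rarer in those who cannot report, a rate restricted to assessable participants would overstate PDPH in the enrolled population. That is a fair reason to report both rates.

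**Conclusion.** The gap is real, but its size is unknown. Eligibility has no age or capacity limit, ascertainment rests on questioning, no alternative method or assessability rule is given, and the SAP divides by everyone with CSF appearance. Participants who cannot report and are not otherwise diagnosed lower the observed rate, towards meeting the criterion.

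The documents do not show that the effect is large or that it will occur at all, because sites may leave vulnerable participants out. At a non-assessable share of 5% to 10% the shift in a true 3.0% rate is 0.15 to 0.3 percentage points, small beside the exact interval. With 150 in the denominator the criterion result changes at 4 events only from 17 non-assessable participants. These figures rest on the assumed shares, equal underlying rates, and no 'Yes' among those who cannot report. The case for acting is that this is a primary safety endpoint, the likely direction favours passing, and the remedy is cheap.

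**What to change.** - **CRF.** Add an answer to the PDPH question: not assessable (unable to report headache or its relation to posture). The study physician judges this for each participant, on ability to report and not on whether a headache was found.
- **Protocol 7.4.1.** State how PDPH is assessed in participants who cannot self-report, including whether a caregiver's account or observation may be used.
- **SAP 5.2.2.** Compute the primary PDPH rate and exact interval among assessable safety participants. This also defines evaluable, as used in Protocol 10.4, for PDPH. Report the number not assessable, and give the rate over all safety participants as a sensitivity analysis.
- **What to avoid.** Do not use age or representative consent as an automatic exclusion. It could drop adolescents who describe symptoms perfectly well, and the listed baseline data and Schedule of Activities do not include who gave consent.

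The cost is one CRF option, a sentence on assessment in the protocol, and a short addition to the SAP. The PDPH denominator becomes slightly smaller and the interval wider: at 4 events, 0.73% to 6.69% with 150 becomes 0.81% to 7.41% with 135. If no such participant enrols, nothing changes. The performance and other adverse-event analyses keep their present populations.
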